6.2.2 Secondary Outcome

In Aim 2, we will assess the effect of the intervention on the proportion of patients with contextual NCCN guideline-concordant care. This approach is modeled after analyses used by [name] et al. in the MedSeq CSER1 project.^{25,26} Operationalization of contextual guideline concordant care: In the primary analysis, we will assess the uptake of contextualized guideline-concordant care taking into account clinically relevant, patient specific circumstances. We will use clinical characteristics from the

EHR to assign each patient to clinical category for which there are discrete NCCN recommendations. Using patient self-reported baseline/T1 and EHR data, following sequencing disclosure, we will create a summary genetically guided care variable ranging from 0-100%. The denominator consists of the total number of contextual guideline-concordant interventions/behaviors possible during a 12-month period following results disclosure for any given patient given his/her germline findings, family history, and clinical characteristics. The numerator consists of the total number of patient-adopted guideline concordant intervention/behaviors completed during a 12-month period following results disclosure. For a patient found to have a pathogenic germline/actionable somatic variant, we will assign benchmarks of genetically guided care derived from evidence based clinical practice guidelines (i.e. NCCN, United States Preventive Services Task Force, or medical society based clinical guidelines). We convene a weekly POTB meeting where a panel of medical geneticists, cancer geneticists, genetic counselors, genetic nurse practitioners, oncologists, gastroenterologists, cardiologist, and hepatologist review cases and develop multidisciplinary contextualized guideline concordant recommendations (chaired by [name]).

In the secondary analyses, we will define guideline concordant as meeting $\geq 75\%$ of recommended guidelines. In sensitivity analyses, we will vary the cutoff for guideline concordance between 50% and 100%.

We will test if the use of HOPE-Genomics will result in higher rates of uptake of evidence-based genetically guided care (e.g., patient receipt of guideline concordant care, cascade testing) than usual care: Our primary goal will be to assess whether or not the uptake of contextual guideline-concordant care differs between the two arms. The primary objective is to test the null hypothesis of no intervention effect on the outcome. We expect that patients in the intervention arm will have higher rate of uptake of contextual guideline-guided care than patients in the control arm. A two-sided Type I error of 0.05 will be used for all statistical tests. We will consider two-sided p-value less than 0.05 as a statistically significant. Patients will be considered concordant ($Y=1$) if they undergo a predetermined percentage of genetically guided care and discordant ($Y=0$) otherwise. Using an intention-to-treat analysis, the proportion of concordant patients will be modeled using the logistic regression approach for binary outcome (PROC LOGISTIC in SAS [Cary, N.C.]). We will use compound symmetry and unstructured working correlation matrix to account for correlation between patients within the same physician. The odds ratio of the concordant patients between the intervention and control arms will be calculated using the group coefficient in the Logistic model. The significance of the coefficient will be tested to determine treatment group difference. In addition, we will use Kauermann and Carroll (KC) correction for robust SEs if the number of physicians is small.¹¹ To evaluate the success of randomization, we will test the differences in characteristics of physicians and patients between the two arms. The Logistic model will include statistically significant characteristics as covariates. Logistic will also be used to model the percentage of the rate of uptake of the genetically guided care per patient, treated as a binomial variable, and include the within-physician correlation, to test for treatment group difference.

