4.0 STUDY PROCEDURES

4.1. Informed Consent and Baseline Survey

Potentially eligible patients will be approached by study team members for verbal informed consent, either by mail/ email, during clinic visits, or by phone. Patients will receive a study packet that will contain an invitation letter, interest postcard, return envelope, and informed consent document. Patients will be randomized into one of three arms immediately after enrollment. Arm 1 is usual care, Arm 2 is return of results only in the HOPE-Genomics tool, and Arm 3 is return of results plus pretest education in the HOPE-Genomics tool.

Arm 1 patients will receive

a pamphlet (20430 Educational Brochure in iRIS) about WES after they enroll. Their clinician will return their genomics test results in a typical manner, without the assistance of the HOPE-Genomics tool.

Arm 2 patients will receive their genomics test results both from their clinician and from the HOPE-Genomics tool but will only view the tool after their results are available. Arm 3 patients will view the HOPE-Genomics tool (containing educational content) before their sequencing results are available. These patients will also receive their genomics test results both from their clinician and from the HOPE-Genomics tool. After completing all study surveys at 9 months post results disclosure, participants in Arm 1 (usual care), will receive access to the HOPE-Genomics tool, which will contain both the educational information and the personalized genomics results.

Table 1: Outcome and covariate data collection

			Patient surveys			MRA
	Baseline	Pre-edu. survey	T1	T2	T3	
Genetic Care outcomes						
MD recommendations						
Screening, surgery, meds			X	X	X	X
Referrals GC, specialists			X	X	X	X
Cascade testing			X	X	X	X
Patient utilization/behavior						
Screening, surgery, meds			X	X	X	X
Consult GC, specialists			X	X	X	X
Inform family members			X	X	X	
Cascade testing			X	X	X	
Patient-centered outcomes						
Recall of results	X		X	X	X	X
Understanding of results			X	X	X	
Genomic knowledge	X	X	X	X		
Engagement in care			X	X	X	
Information seeking				X		
Psychosocial impact	X		X	X	X	
Follow up outcomes						
HOPE-Genomics usability			X	X		
Satisfaction with MD-patient communication and care			X	X		
Covariates						
Socio-demographics	X					X
Clinical information						X
Other (e.g., health literacy)	X					X

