Medical record abstraction (MRA); Post disclosure: 10 days (T1); 3 months (T2); 9 months (T3); Medications (Meds); Genetic counseling (GC); Physician (MD)

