4.3 Tool Access and Patient Pre-Education Survey

After enrollment, all participants will be provided with a hard-copy or electronic educational pamphlet about whole-exome sequencing (WES). Patients in the Return of Results plus Pre-test Education arm will be provided with login and dual-factor authentication instructions and have immediate access to educational content in the tool, with their sequencing results to become available in the tool shortly after their results are available in Epic. Patients in the Return of Results Only arm will not be able to see tool content until their genomic test results are available (e.g., ~2-6 weeks after sample collection). Patients in the Usual Care arm will have access to the tool content after completing all study surveys, approximately ~9 months after their sequencing results are available.

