4.4 Results Disclosure

We expect results to be available within ~3-14 days of sample acquisition. We will monitor the patients' laboratory data to see when results have been finalized. Lab results and variant interpretations for the HOPE Genomics intervention will be stored in a custom genomic database designed by COH Research Informatics. All results will be validated by study staff before data are input into the HOPE-Genomics tool. All clinicians will receive results through the EHR. Additionally, clinicians with patients in the intervention arm will also be able to view their patients' results through the HOPE-Genomics after individual-level patient data have been entered into HOPE-Genomics. Results will be available to patients in the HOPE-Genomics app approximately 3-14 days after they are available in the EHR.

At this time, we will ask patients in the Return of Results Only intervention arm, (Arm 2) and the Return of Results + Pre-Test Education arm (Arm 3) to log into the HOPE-Genomics tool on their own time. Study staff will provide patients with instructions to create an account and log into the tool using dual-factor authentication. Study staff will track patients' tool access through Google Analytics and call or send automated RedCap reminders to encourage tool use, if necessary. Study staff will track patients' tool access through Google Analytics and call and/or send automated REDCap reminders to encourage tool use, if necessary. In addition, the study staff will be available to help patients access HOPE-Genomics at subsequent clinic/infusion visits or via secure web conference at any point in time following the disclosure of their test results until the end of the study (with coordination with the study team).

Patients in the control arm (Arm 1) will have their results returned in clinic by their provider, with no changes to the clinician's typical delivery method. Patients will be provided an educational pamphlet that generally describes sequencing and will granted access to the HOPE-Genomics tool with their results after completing all follow-up study surveys, approximately 9 months after their results are in the EHR.

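### Aim 2 counts guideline-concordant care over 12 months, but the usual-care arm is scheduled to receive the tool at about 9 months, and no stated analysis handles the overlap

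*Combined protocol and SAP*

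**What the plan says.** Section 6.2.2 builds a 0-100% concordance score for each patient. On the bottom of the fraction: "The denominator consists of the total number of contextual guideline-concordant interventions/behaviors possible during a 12-month period following results disclosure". On the top: "The numerator consists of the total number of patient-adopted guideline concordant intervention/behaviors completed during a 12-month period following results disclosure".

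Three sections date the control arm's access to the tool:

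- Section 4.1: "After completing all study surveys at 9 months post results disclosure, participants in Arm 1 (usual care), will receive access to the HOPE-Genomics tool". It adds that this version holds both the educational content and the patient's own results.
- Section 4.3: "Patients in the Usual Care arm will have access to the tool content after completing all study surveys", put at roughly 9 months after results are available.
- Section 4.4 grants Arm 1 the "HOPE-Genomics tool with their results after completing all follow-up study surveys, approximately 9 months after their results are in the EHR".

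Section 4.5.3 says that usual-care participants will view their results in the tool at that point. The Table 1 footnote puts the last survey (T3) at 9 months. There is no 12-month survey.

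For the analysis, Section 6.2.2 specifies an intention-to-treat logistic regression. It also says: "In sensitivity analyses, we will vary the cutoff for guideline concordance between 50% and 100"%. Section 6.2.3 adds a linear regression on the same score.

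**The concern.** Aim 2 asks whether the tool raises uptake of genetically guided care compared with usual care. After about month 9, Arm 1 is no longer under usual care alone: by design it has the tool with personal results. Months 9 to 12 therefore compare earlier with later tool access, yet they are scored as tool against no tool.

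If the tool works, some of the care that Arm 1 takes up in that stretch will be due to the tool but will count for usual care. That pulls the contrast toward no difference. A null or weak Aim 2 result would then be hard to read, because an ineffective tool and a control group that was partly treated would look alike. A 9-month count chosen only after the results are known would look selective, so the plan is the place to settle it.

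**Working it through.** **Step 1. Dates.** Outcome window: 12 months (6.2.2). Arm 1 access: about 9 months, after the last survey (4.1, 4.3, 4.4). With access at month m, overlap = max(0, 12 − m). At m = 9 this is 3 months, and 3/12 = 25% of the window. It shrinks as T3 is returned later. It is zero for a patient who never completes the surveys, who is not scheduled for access.

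**Step 2. Does any stated analysis deal with it?**

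- Intention-to-treat keeps patients in their assigned arm. It does not address control exposure inside the outcome window.
- The cutoff varied from 50% to 100% is a share of recommended care, not a time.
- The linear regression in 6.2.3 changes the model. The score and its 12 months stay the same.
- Section 4.6 abstracts records throughout the study, with no stop at Arm 1 access.

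None of these shortens, censors or re-windows the count.

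**Step 3. Where it can act.** With no survey after 9 months, behaviour in months 9-12 enters only through the medical record. The overlap therefore works through record-captured items. Self-report collected up to T3 precedes access.

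**Step 4. The plan's own power figure.** The only one is for Aim 1 (6.2.1): 39% vs 54%, n = 130 vs 260, two-sided 0.05.

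- Pooled rate = (130×0.39 + 260×0.54)/390 = 0.49
- Null SE = √[0.49×0.51×(1/130 + 1/260)] = 0.0537
- Alternative SE = √[0.39×0.61/130 + 0.54×0.46/260] = 0.0528
- Power = Φ[(0.15 − 1.96×0.0537)/0.0528] = Φ(0.848) = 80.2%, which reproduces the stated 80%.

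**Step 5. Illustration only.** The plan gives no rates, event timing or analysable number for Aim 2, so I borrow the Aim 1 inputs. Let Hc = −ln(0.61) = 0.494 and Ht = −ln(0.46) = 0.777. Let L be the share of cumulative hazard falling in months 9-12, and a the share of controls who take on the full tool effect at month 9.

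- 9-month rate in each arm = 1 − exp[−H(1−L)]
- 12-month control rate = 1 − exp[−Hc(1−L)] × [(1−a)exp(−Hc·L) + a·exp(−Ht·L)]

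| L | 12-month power, a = 0 / 25 / 50 / 100% | 12-month gap in points, a = 50 / 100% | 9-month rates; gap; power | a at which 9-month power equals 12-month power |
|---|---|---|---|---|
| 25% | 80.2 / 74.2 / 67.4 / 52.4% | 12.9 / 10.8 | 31.0 vs 44.1%; 13.2; 71.3% | 36% |
| 10% | 80.2 / 77.8 / 75.3 / 70.0% | 14.2 / 13.3 | 35.9 vs 50.3%; 14.4; 77.2% | 32% |
| 5% | 80.2 / 79.0 / 77.8 / 75.3% | 14.6 / 14.1 | 37.5 vs 52.2%; 14.7; 78.8% | 30% |

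The table shows two things. Dilution ranges from slight to substantial, depending on quantities nobody knows. A 9-month main window gains power only if about 30-36% or more of controls take on the full effect; below that it loses power.

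**The case against.** The strongest case against acting is that the effect may be small. Access follows return of T3, which can be late: follow-up survey reminders go out every 2 weeks and non-responders are contacted up to five times. Behaviour needs time to change after access, which the illustration ignores. The outcome is secondary, the bias is conservative, and cutting the window to 9 months discards late events. The borrowed rates belong to recall, a different outcome, and the model treats a multi-item score as one event and ignores clustering by physician. All of this stands. It limits the size of the problem and argues against imposing a shorter main window. It does not remove the overlap, which rests on dates alone.

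Three stronger readings are tempting, and the documents do not support them.

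- A reader might infer that Aim 2 power falls to about 52%. That needs every control to adopt the full effect at once and a quarter of the hazard to fall in the last quarter of the window, on rates that the plan never states for Aim 2.
- A reader might infer from the end of Section 4.3 that Arm 1 sees the tool as soon as results are loaded, so that most of the window is contaminated. That sentence only says access does not come before results are in the tool. Sections 4.1, 4.3 and 4.4 give about 9 months. The garbled survey label in 4.5.3 sets no other date.
- A reader might infer that 12 months is the wrong window and must be replaced. The table shows that this is a trade-off.

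**Conclusion.** The point holds as a matter of dates. For Arm 1 patients who finish on schedule, up to 3 of the 12 months counted for Aim 2 follow planned access to the tool with personal results, and nothing in the analysis plan addresses it. If the tool works, the resulting bias on the Aim 2 contrast is toward no difference.

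Confidence is high on the overlap and its direction, and low on its size. The size depends on how many controls complete the surveys and use the tool, how quickly they act, and how much recorded care falls after month 9. The documents give none of these. The bias may be modest. It cannot produce a false positive, and the 10-day recall outcome of Aim 1 is not touched. This should be fixed because the remedy is cheap and makes the Aim 2 result easier to interpret; it does not invalidate the design.

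**What to change.** In Section 6.2.2, keep the 12-month count as the main analysis if preferred, and make two additions.

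1. Pre-specify a sensitivity analysis that counts both numerator and denominator only over the first 9 months after disclosure, in all three arms. For an Arm 1 patient who gets the tool earlier than that, stop the count at access. Arms 2 and 3 keep the same 9-month limit. Use the same disclosure date as the 12-month count.
2. State that the 12-month result includes scheduled control access to the tool.

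Cost: no extra patients, visits or surveys. Each patient's benchmarks must be derived a second time, for 9 months, because the denominator is what was possible within the window. The sensitivity count drops late behaviours and so is less precise, and the 12-month result remains diluted to whatever extent controls adopt the tool.

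Making 9 months the main window, or opening Arm 1 access only at 12 months, would also remove the overlap. Both are options for the sponsor, not required corrections.

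Separately, two figures in Section 6.1 need reconciling. Participation of about 7 months is shorter than both the 9-month survey and the 12-month window. The 26-month total, which includes analysis, is shorter than 16 months' accrual plus 12 months' follow-up (16 + 12 = 28), even before adding the time from enrolment to results.

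### Aim 2 names ordinary logistic regression but promises GEE features it cannot supply, and does not say which standard errors the binomial score test uses, so run literally that test is too liberal

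*Combined protocol and SAP*

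**What the plan says.** All of this is in section 6.2.2 of the combined protocol and SAP, unless noted.

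- **Model and software, binary outcome:** "the proportion of concordant patients will be modeled using the logistic regression approach for binary outcome (PROC LOGISTIC in SAS [Cary, N.C".
- **Treatment effect:** the odds ratio "will be calculated using the group coefficient in the Logistic model", and that coefficient is tested at a two-sided 0.05.
- **Clustering:** "We will use compound symmetry and unstructured working correlation matrix to account for correlation between patients within the same physician". Two structures are named, with no rule for choosing between them.
- **Robust SEs:** they appear only through a conditional correction: "we will use Kauermann and Carroll (KC) correction for robust SEs if the number of physicians is small". The section gives neither a threshold for small nor an expected number of physicians.
- **Score outcome:** logistic regression is also to be used for the "percentage of the rate of uptake of the genetically guided care per patient, treated as a binomial variable, and include the within-physician correlation". Correlation among one patient's own items is not mentioned, and neither is overdispersion.
- **Denominator of the score:** "The denominator consists of the total number of contextual guideline-concordant interventions/behaviors possible during a 12-month period". It varies by patient, and no typical value is given.

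GEE is not named for Aim 2. Section 6.2.3 names it for test-related distress. Section 6.2.3 also analyses the 0-100% concordance score by linear regression, as a sensitivity analysis.

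**The concern.** The named procedure and the promised features do not fit together. Maximum-likelihood logistic regression treats observations as independent and has no working correlation matrix. A working correlation and KC-corrected sandwich SEs are parts of GEE. An analyst who follows the named software delivers something other than the clustering paragraph describes. An analyst who follows the clustering paragraph has to abandon the named software.

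The unstructured matrix is a separate defect. It gives each pair of positions in a cluster its own correlation, which makes sense for visits 1, 2 and 3 but not for a physician's patients, who have no shared positions and whose number differs between physicians.

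The third issue is the score. A binomial model counts a patient's care items as independent trials. Counselling, informing relatives and cascade testing in the same patient are plausibly correlated. If so, model-based binomial SEs are too small. At stake is the error rate of one form of the Aim 2 comparison, and the credibility of a model that the analyst would have to reinterpret after the data are in.

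**Working it through.** **Inputs from the documents.** 130 usual-care and 260 intervention patients (section 6.2.1); individual randomization after enrollment (section 4.1); two-sided alpha 0.05 (section 6.2.2). Using 130 vs 260 for Aim 2 is an assumption, because section 6.2.2 gives no sample size.

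**The plan's only power figure.** This is for Aim 1: 39% vs 54%. The pooled proportion is (130×0.39 + 260×0.54)/390 = 0.49. The null SE is √[0.49×0.51×(1/130 + 1/260)] = 0.0537, and the alternative SE is √[0.39×0.61/130 + 0.54×0.46/260] = 0.0528. Power = Φ[(0.15 − 1.96×0.0537)/0.0528] ≈ 80.2%, so the stated 80% reproduces. Aim 2 has no corresponding figure to check.

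**Unstructured matrix.** The number of correlations for a cluster of m patients is m(m−1)/2. Physician counts are assumed:
- 30 physicians: 390/30 = 13 patients each, 13×12/2 = 78 correlations.
- 10 physicians: 390/10 = 39 patients each, 39×38/2 = 741 correlations.

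The counts only illustrate the burden. The lack of a common ordering would rule the structure out even with small clusters.

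**Binomial score, closed form.** For m items per patient with within-patient correlation ρ, the design effect is DE = 1 + (m−1)ρ. The model-based SE is 1/√DE of the true one, and the actual two-sided type I error is 2[1 − Φ(1.96/√DE)]. Both m and ρ are assumed.

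| m | ρ | DE | SE ratio | Type I error |
|---|---|---|---|---|
| 2 | 0.1 | 1.1 | 0.95 | 6.2% |
| 3 | 0.2 | 1.4 | 0.85 | 9.8% |
| 4 | 0.3 | 1.9 | 0.73 | 15.5% |
| 6 | 0.5 | 3.5 | 0.53 | 29.5% |

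**Simulation under no treatment effect.** 130 vs 260 patients randomized individually; 15 or 40 physicians; 2-6 items per patient; latent variance share 0.05 or 0.15 for physician and 0.1, 0.3 or 0.5 for patient; 2000 runs per scenario. All of these except the arm sizes and the unit of randomization are assumptions. The latent shares are not on the same scale as ρ above. Monte Carlo error near 5% is √(0.05×0.95/2000) ≈ 0.5 percentage points. The clustered SEs here carry no KC correction.

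| Outcome and SE | SE / true SD | Type I error |
|---|---|---|
| Binary, plain logistic | 0.97-1.01 | 4.1-5.4% |
| Binary, physician-clustered, 40 physicians | 0.97-1.00 | 5.1-6.6% |
| Binary, physician-clustered, 15 physicians | 0.96-0.99 | 6.9-7.9% |
| Score, model-based binomial | 0.62-0.89 | 7.3-21.6% |
| Score, physician-clustered, 40 physicians | 0.97-1.02 | 5.1-6.0% |
| Score, physician-clustered, 15 physicians | 0.96-1.01 | 6.6-7.9% |
| Score, patient-level sandwich | 0.98-1.03 | 4.2-5.5% |

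A second null simulation with the same arm sizes (latent shares 0.05 physician and 0.40 patient, 2000 runs) gave 12-21% for model-based score SEs and 5.6-6.6% for physician-clustered SEs with the KC correction.

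**Reading the results.** Physicians have patients in every arm, so a physician effect largely cancels from the binary comparison. Correlation among a patient's items does not cancel, because each patient sits in one arm. Clustering on physician covers it, since patients are nested within physicians.

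**The case against.** The strongest reply is that the intent is plain. Working correlation, robust SEs and the KC correction all point to GEE, which section 6.2.3 names in similar terms for distress. The score model is expressly to include within-physician correlation. If physician-clustered robust SEs are what will be computed, they also absorb the item correlation, and the 7-22% does not arise. The linear regression in section 6.2.3 uses one value per patient, makes no assumption about independent items, and would expose a false positive from a naive binomial fit. The inputs behind the error rates are assumed, and mild cases (2 items, ρ = 0.1) give only 6.2%.

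Most of this stands, and it limits the point. Two stronger readings that a reader might infer are not supported:

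- **That the binary Aim 2 test is invalid because clustering is ignored.** Patients, not physicians, are randomized, and plain logistic SEs hold close to 5%.
- **That the score model necessarily understates its SEs.** It does so only with model-based SEs, and the plan does refer to within-physician correlation and robust SEs.

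The reply does not remove the mismatch. The only software named for Aim 2 fits no working correlation, and robust SEs are mentioned only under an undefined condition. The linear regression is a partial check, since it is labelled a sensitivity analysis and does not correct the binomial p-value. The score is also not clearly peripheral: the operationalization text in section 6.2.2 places the 0-100% summary under its primary analysis and the 75% cutoff under secondary analyses.

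**Conclusion.** The point holds as a specification defect with a conditional numerical consequence. The named procedure cannot deliver the promised working correlation or KC-corrected SEs, and the unstructured matrix cannot sensibly be fitted to patients within physicians. Neither statement depends on an assumed number.

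The size differs by outcome. For the binary outcome the effect on type I error is negligible. For the binomial score, the same plan can give a test at about 5-6% (robust SEs, 40 physicians) or one at 7-22% (model-based SEs), depending on a choice the plan leaves open. Those ranges rest on assumed item counts, correlations and physician numbers, and on all 390 patients contributing. The direction, understated SEs when a patient's items are positively correlated, does not depend on the particular values.

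**What to change.** In section 6.2.2:

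1. Replace PROC LOGISTIC with a single GEE logistic model: physician as cluster, exchangeable (compound symmetry) working correlation, KC-corrected robust SEs. Name a routine that actually computes the KC correction.
2. Delete the unstructured option.
3. Apply the KC correction in all cases, so that a small number of physicians needs no definition. This matters for the binary outcome too: with 15 physicians, uncorrected clustered SEs gave 6.9-7.9%, worse than plain logistic regression.
4. State that the binomial score model uses the same physician-clustered, KC-corrected robust SEs and not model-based ones. A beta-binomial model with only a patient-level dispersion term would lose the physician correlation the plan promises, so it should not be substituted unless it keeps that as well.
5. Keep the linear regression of the score in section 6.2.3 as a check.

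The cost is a few sentences of SAP text, with no change to data collection or sample size. Score confidence intervals become wider and p-values somewhat less favourable than under model-based SEs.
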